5.2.2. Analyses of Non-Longitudinal Continuous Data

The non-longitudinal continuous data will be analyzed by ANCOVA with treatment as the factor and baseline disease severity as covariates. When modeling the change from baseline values, the variable for visit will start with the first post-baseline visit, and the actual baseline value will be included as a covariate. At each visit, estimates of least square mean (LSM) values and the LSM differences between treatment groups will be derived from the model. The corresponding p-values and 95% confidence intervals will also be derived from the model.

5.2.3. Analyses of Longitudinal Continuous Data

Mixed-effect, repeated measures (MMRM) models will be used. The fixed effects of treatment, visit, treatment-by-visit interaction and baseline disease severity will be included. Visit will be modeled as a categorical covariate. Unstructured covariance matrix will be assumed for the model errors. Compound symmetry covariance matrix will be used if the model with unstructured covariance doesn't converge.

When modeling the change from baseline values, the variable for visit will start with the first post-baseline visit, and the actual baseline value will be included as a covariate. At each visit, estimates of least square mean (LSM) values and the LSM differences between treatment groups will be derived from the model. The corresponding p-values and 95% confidence intervals will also be derived from the model. In the model all patients with baseline data are used for estimating baseline covariate effects and adjusting LS means.

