- If hypothesis of no difference in NRS4 at Week 2 between 100 mg QD and dupilumab is rejected in Sequence A, compare 100 mg QD versus dupilumab at Day 15, Day 14, Day 13, Day 12, ..., Day 2, in that order. For this sequence, any hypotheses after the last time point (or Day) for which all four comparisons (200 mg QD versus placebo, 200 mg QD versus dupilumab, 100 mg QD versus placebo and 100 mg QD versus dupilumab) are significant will not be considered significant.

All hypotheses in each of the four sequences will be assessed at the 5% level of significance. Although this testing procedure will not protect the Type-I error for the family of all possible comparisons, it will provide Type-I error protection for the family of NRS4 time points within each treatment group and treatment groups within each time point.

Hypotheses corresponding to all secondary and other endpoints will be tested at the 5% level of significance without any adjustment for multiplicity.

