6.4.3. Continuous Endpoints

- Endpoints:
 - Weeks 2, 4, 8, 12 and 16 Change from Baseline and Percent Change from Baseline in % BSA, Total SCORAD score, SCORAD subjective assessments of sleep loss (VAS);
 - Weeks 2, 4, 8, 12 and 16 Percent Change from Baseline in Total EASI Score;
 - Percent Change from Baseline in Severity of Pruritus NRS each day from Days 2-15, Weeks 4, 8, 12 and 16;

- Summary: Change from baseline and/or percent change from baseline at each specified time points;
- Population: FAS;
- Statistical Method: MMRM in [Section 5.2.3](#);
- Missing Data: Observed Data.

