9. APPENDICES

Appendix 1. Summary of Clinical Efficacy Analyses

Efficacy Endpoints	Population	Analysis Method	Missing Data Imputation	Primary Analysis for Co-primary Endpoints
Week 12 IGA Response	FAS	CMH	NR	Yes
Week 12 IGA Response	PPAS	CMH	NR	No
Week 12 IGA Response	FAS	CMH	TP	No
Week 12 EASI-75 Response	FAS	CMH	NR	Yes
Week 12 EASI-75 Response	PPAS	CMH	NR	No
Week 12 EASI-75 Response	FAS	CMH	TP	No
Week 2 NRS4 for severity Response	FAS	CMH	NR	
Week 16 IGA Response	FAS	CMH	NR	
Week 16 EASI-75 Response	FAS	CMH	NR	
Days 2-15, Weeks 4, 8, 12 and 16 NRS4 for Severity Response	FAS	CMH	NR	
Time to NRS4 for severity	FAS	Time to Event		
Weeks 2, 4 and 8 IGA Response	FAS	CMH	NR	
Weeks 2, 4, 8, 12 and 16 EASI-50, EASI-90, EASI-100 Response	FAS	CMH	NR	
Weeks 2, 4 and 8 EASI-75 Response	FAS	CMH	NR	
Weeks 2, 4, 8, 12 and 16 Percent CFBL in Total EASI Score	FAS	MMRM	OD	
Days 2-15, Weeks 2, 4, 8, 12 and 16 Percent CFBL in NRS for severity	FAS	MMRM	OD	
Weeks 2, 4, 8, 12 and 16 Percent CFBL in %BSA	FAS	MMRM	OD	
Weeks 2, 4, 8, 12 and 16 CFBL and Percent CFBL in SCORAD Total Score	FAS	MMRM	OD	
Weeks 2, 4, 8, 12 and 16 SCORAD50 Response	FAS	CMH	NR	
Weeks 2, 4, 8, 12 and 16 SCORAD75 Response	FAS	CMH	NR	
Weeks 2, 4, 8, 12 and 16 CFBL and Percent CFBL in SCORAD (VAS) for sleep loss	FAS	MMRM	OD	
CFBL=Change from baseline; CMH=Cochran-Mantel-Haenszel; ANCOVA=Analysis of Covariance; MMRM=Mixed-effect Model Repeated Measures; NR=Non-Responder; OD=Observed Data; TP=Tipping Point				

090177e1937d0b4e\Approved\Approved On: 18-May-2020 15:17 (GMT)

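### The only MMRM fallback is compound symmetry with model-based standard errors, which could misstate visit-specific intervals in either direction, chiefly for percent change in pruritus NRS

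*SAP*

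**What the plan says.** SAP 5.2.3 states the starting point, "Unstructured covariance matrix will be assumed for the model errors", and the single alternative: "Compound symmetry covariance matrix will be used if the model with unstructured covariance" fails to converge. On inference it says "The corresponding p-values and 95% confidence intervals will also be derived from the model". It names no intermediate structure and no empirical (sandwich) standard error. Protocol 9.2.4 also calls for an MMRM but does not discuss covariance.

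The endpoints sent to this model differ greatly in size:

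- **Pruritus NRS.** SAP 6.4.3 lists "Percent Change from Baseline in Severity of Pruritus NRS each day from Days 2-15, Weeks 4, 8, 12 and 16", which is 18 time points. SAP 3.2.2 gives the same set.
- **Pruritus NRS in the Appendix 1 summary table.** The row reads "Days 2-15, Weeks 2, 4, 8, 12 and 16 Percent CFBL in NRS for severity", which adds Week 2 and makes 19.
- **EASI.** SAP 6.4.3 lists "Weeks 2, 4, 8, 12 and 16 Percent Change from Baseline in Total EASI Score", which is five visits. BSA, SCORAD and PtGA use the same five.
- **Other PROs.** DLQI has three visits. HADS, POEM and EQ-5D-5L have two. PSAAD is averaged by week up to Week 16.

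Appendix 2 of the SAP takes Days 2-15 NRS from the actual day. It takes Week 2 NRS from the record in the Day 2 to 22 window that lies closest to Day 15.

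On error control, SAP 5.1 says "Hypotheses corresponding to all secondary and other endpoints will be tested at the 5% level of significance without any adjustment for multiplicity".

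**The concern.** Compound symmetry treats the spread at Day 2 and at Week 16 as equal, and the Day 2/Day 3 correlation as equal to the Day 2/Week 16 correlation. In the 18-point NRS model, 14 of the 18 points fall in the first 15 days, so the pooled variance mostly reflects early records. If the SD rises with time, late intervals come out too narrow and the earliest too wide. If it falls, the reverse holds.

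The fallback matters only if the unstructured fit fails. The Week 2 entry in Appendix 1 opens a route to that. For a subject with a Day 15 diary entry, the windowed Week 2 value is the same record, so a model holding both has two nearly identical columns and a near-singular covariance matrix.

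At stake are the reported intervals, and the p-values against placebo, for percent change in itch at individual time points. If the fit fails, the SAP prescribes compound symmetry, and any better choice made after unblinding would be post hoc.

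**Working it through.** The plan states no MMRM figure (no visit SD, interval width or power), so there is nothing to reproduce.

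**Inputs from the documents.** Time points are from SAP 6.4.3 and Appendix 1. Arms are 200/200/200/100 up to Week 16 (SAP 2.2).

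**Assumptions.** Day 2 SD is set to 1 and Week 16 SD to k, with k from 0.8 to 2.25. The SD either changes linearly from Day 2 to Day 113 or levels off at Day 29.

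**Step 1: size of the unstructured matrix.** With m time points it has m(m+1)/2 parameters.

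- m = 5: 5×6/2 = 15.
- m = 18: 18×19/2 = 171.
- m = 19 (Week 2 added): 19×20/2 = 190.
- m = 16 (PSAAD, if each week is a visit level): 16×17/2 = 136.

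**Step 2: interval width under compound symmetry, complete data.** The fitted SE at visit j uses the mean of the visit variances, while the correct SE uses the variance at j:

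r_j = sqrt(mean of SD²) / SD_j, and coverage = 2Φ(1.96 r_j) − 1.

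Worked case, k = 1.5, linear, 18 points: SD at day t is 1 + 0.5(t − 2)/111. Variances over Days 2-15 sum to 14.836. Those at Weeks 4, 8, 12 and 16 are 1.258, 1.557, 1.888 and 2.250, summing to 6.953. The mean is (14.836 + 6.953)/18 = 1.2105, and its square root is 1.100. At Week 16, r = 1.100/1.5 = 0.733, and coverage is 84.9%.

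Week 16 width ratio, with coverage in brackets:

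| k | 18-point, linear | 18-point, plateau | 5-visit, linear | 5-visit, plateau |
|---|---|---|---|---|
| 0.8 | 1.21 (98.2%) | 1.15 (97.6%) | 1.12 (97.2%) | 1.03 (95.6%) |
| 1.0 | 1.00 (95.0%) | 1.00 (95.0%) | 1.00 (95.0%) | 1.00 (95.0%) |
| 1.1 | 0.93 (93.1%) | 0.95 (93.7%) | 0.96 (93.9%) | 0.99 (94.8%) |
| 1.25 | 0.84 (90.0%) | 0.89 (91.7%) | 0.91 (92.4%) | 0.98 (94.5%) |
| 1.5 | 0.73 (84.9%) | 0.81 (88.8%) | 0.85 (90.3%) | 0.97 (94.2%) |
| 2.0 | 0.61 (76.6%) | 0.73 (84.5%) | 0.78 (87.2%) | 0.95 (93.8%) |
| 2.25 | 0.57 (73.3%) | 0.70 (82.9%) | 0.76 (86.1%) | 0.95 (93.7%) |

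At Day 2 in the 18-point model the error runs the other way: the ratio is 1.05 to 1.45 for k from 1.25 to 2.0.

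**Step 3: with dropout.** REML compound-symmetry fits were simulated with decaying correlation and about 12% MAR dropout by Week 16, 300 runs per scenario. Monte Carlo error is about 1 to 3 points on coverage and 4% on the SE ratio. Week 16 model SE over empirical SE in the 18-point model:

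- k = 1.0: 0.90-0.94, coverage 91-93%.
- k = 1.25: 0.85-0.88, coverage 91-92%.
- k = 1.5: 0.74-0.80, coverage 85-87%.
- k = 2.0: 0.56-0.74, coverage 71-85%.

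The k = 1.0 result suggests that a decaying correlation alone costs some coverage. Across the same scenarios, five-visit coverage at Week 16 was 86-97%.

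**Step 4: does the unstructured fit fail?** In simulated ML fits of the 18-point model (700 subjects, rounded 0-10 scores, 6% intermittent missingness, 12% dropout, k from 0.8 to 2.0), all 240 of 240 converged. With Week 2 added as a nineteenth visit, 12 of 16 failed, and the fits that did converge were numerically singular.

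**The case against.** The strongest case against is that this branch may never be reached. In simulation, 171 parameters with 700 subjects were no obstacle, and five-visit models with 15 parameters are safer still. The failure route found needs Day 15 and Week 2 in one model, and the SAP never says that. Sections 3.2.2 and 6.4.3 omit Week 2, only the summary table adds it, and the separate derivation rules in Appendix 2 are compatible with separate daily and visit analyses. This stands, and it confines the point mainly to pruritus NRS. It does not remove it: Appendix 1 and 6.4.3 disagree, and the literal Appendix 1 list is the one that breaks the fit.

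A second objection is that no controlled conclusion is at risk. The co-primary and key secondary endpoints use CMH. MMRM endpoints lie outside the multiplicity procedure, and SAP 5.2 disclaims statistical significance except where noted. This also stands. The intervals and p-values would still be reported, and should be right.

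A reader might infer that late-visit intervals would be far too narrow, with type I error of 17% or so. The documents do not support that. They give no visit SDs and nowhere say that the spread of percent change grows over time. A 17% figure needs a steep assumed rise, for example SD 20 to 45 levelling by Day 29. With growth of 10-25%, the shortfall in the linear case is 7-16%, and if the SD falls the interval is too wide.

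**Conclusion.** The point holds as a conditional weakness. If the unstructured model fails and visit variances differ, the prescribed fallback misstates visit-specific intervals and p-values, by an amount and in a direction that the documents do not let us determine. For the 18-point NRS model with complete data, the Week 16 width runs from 21% too wide (k = 0.8) to 43% too narrow (k = 2.25, linear). These figures rest entirely on assumed SD paths. In the five-visit models the error is smaller, at most 22% too narrow even if the SD doubles, and the fallback is unlikely to be needed.

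The Day 2 to Week 16 span applies only to percent change in pruritus NRS. Weekly PSAAD is also a large model and is collected only in selected countries (Protocol 7.10.8 and Schedule of Activities), so it has fewer than 700 subjects, but its convergence was not tested. The trial's main conclusions are not affected. The change is worth making because it is cheap and settles the choice before unblinding.

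**What to change.** 1. In SAP 5.2.3, replace the single fallback with an ordered list of heterogeneous-variance structures, for example heterogeneous Toeplitz, then heterogeneous AR(1), then heterogeneous compound symmetry. The particular order is a matter of judgement; what matters is fixing it in advance. Use sandwich standard errors for any structure other than unstructured.
2. Reconcile the Appendix 1 row for percent change in NRS with 6.4.3, so that no record enters the model twice. One way is to fit Days 2-15 (14 points, 14×15/2 = 105 parameters) separately from the clinic visits at Weeks 2, 4, 8, 12 and 16 (15 parameters).

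With visit-specific variances, the complete-data width ratio is 1.00 and coverage 95% by construction. This was not simulated under dropout. The cost is a few lines of SAP text and some programming, with no new data. One limit remains: sandwich errors correct the standard error but do not remove bias in the estimates from a wrong working covariance under MAR dropout, which is why the heterogeneous structures should come first.

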5.2.4. Analyses for Categorical Data

The frequency and percentage for each category will be presented.

5.2.5. Analyses for Time to Event Data

For a subject who experiences the event, the time to event will be the study day corresponding to the actual date of the event or the earliest visit date at which the subject has already experienced the event. For all subjects who have not experienced the event, their time to event will be right censored at the last available measurement time (or visit) used to define whether the subject experienced the associated event.

Time-to-event endpoints will be summarized using the Kaplan-Meier method and estimated survival curves will be displayed graphically. Graphs will describe the number of patients at risk over time. The median and quartiles will be estimated by the Kaplan-Meier method. 95% CIs for the median and quartiles will also be provided.

The log-rank test (stratified using baseline disease severity) p-value will be used for comparing time to event data between treatment groups.

090177e1937d0b4e\Approved\Approved On: 18-May-2020 15:17 (GMT)

5.2.6. Analyses of Tier-1 and Tier-2 Events

Number and percentage of subjects with AEs over the duration of treatment will be provided for each treatment group. Tier-1 events will be analyzed using methods proposed by Chan and Zhang (1999). Tier-2 events will be analyzed using asymptotic methods proposed by Miettinen and Nurminen (1985). Risk differences (each PF-04965842 dose group compared to placebo, and each PF-04965842 dose group compared to dupilumab) and 2-sided 95% confidence intervals will be reported. P-values will also be reported for Tier-1 events. Tier-3 events will not be summarized separately but included within the summary of all AEs.

5.3. Methods to Manage Missing Data

In general, for analyses using descriptive statistics, missing values will not be imputed. In addition, for safety endpoints, missing values will not be imputed. Other methods for handling missing values are discussed below.

5.3.1. Binary Endpoints

For binary endpoints analyzed at each scheduled visit separately, visit windows (see [Appendix 2](#)) will be used to map all observed data into nominal visits. After mapping, for subjects who drop out for any reason, any data will be defined as “non-responsive” at all subsequent visits after the last observed value; for other subjects, any observations missing intermittently (including baseline values) will be considered missing completely at random (MCAR) and will remain missing in the analysis.

Additional analyses that are will utilize the longitudinal nature of the binary endpoint. A Generalized Linear Mixed Model (GLMM) will be fit to the observed data (ie, without defining missing data due to dropout as “non-response”). The binary outcome will be modeled using a logistic-normal distribution. Fixed factors will include treatment (PF-04965842 200 mg QD and 100 mg QD, dupilumab and the placebo group), visit (Weeks 2, 4, 8, 12 and 16) and treatment-by-visit interaction. Visit will be modeled as a categorical covariate. A subject-specific random intercept will be used to model the correlation within a subject over time (see [Appendix 3](#)). Missing observations for the active groups (PF-04965842 200 mg QD and 100 mg QD, dupilumab) will be imputed multiply using a tipping point analysis to estimate the treatment effect under the assumption that the missing data mechanism is missing at random (MAR) or more generally, is missing not at random (MNAR). Using the estimated posterior predictive distribution of the GLMM model parameters obtained using Markov Chain Monte Carlo (MCMC) methods, estimates of the posterior predictive probability of response will be calculated for each treatment group. For subjects with missing data at a visit, the posterior predictive response probability in each active group will be re-defined as a weighted linear combination of the posterior predictive response probability from this group and the posterior predictive response probability from the placebo group, where the missing observations in placebo group are assumed to be missing at random (MAR) (see [Appendix 3](#)). These weights are fixed MNAR quantities for the active groups. A single imputation of the missing value will be sampled from a Bernoulli distribution with this corresponding shifted / re-defined probability of response for the active groups. This imputation will be repeated multiple times with different MCMC samples to obtain multiple completed datasets. For each such completed dataset, the estimates of the

proportions and CMH-weighted difference of proportions between each active group and placebo will be obtained along with the associated standard errors using the methods in [Section 5.2.1](#). Rubin's rule (Rubin, 1987) will be used to combine the multiple estimates and standard errors across the imputed datasets and provide p-values.

The above analysis can be repeated for different combinations of MNAR quantities which will be applied to the probability of response to assess when the conclusion might change (ie, tipping). Two important scenarios are included in the tipping point analysis framework. When the MNAR quantities are zero and the posterior predictive probabilities in the active dose groups are not shifted, results are obtained under an assumption of MAR for the missing data mechanism. Alternatively, at the other extreme, when the MNAR quantities are 1.0 for each active dose group, results are obtained under an assumption that the distribution of the missing responses after discontinuation of each active group is the same as that of the missing responses on the placebo arm. More detailed descriptions are provided in [Appendix 3](#).

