5.2.1. Analyses for Binary Data

Binary data at each scheduled visit will be analyzed by two approaches: (1) the test of hypothesis (and the p-value) of no difference between two treatment groups will be conducted by the Cochran-Mantel-Haenszel (CMH) statistic adjusting for baseline disease severity (moderate or severe); p-values from the CMH statistic will be used to test the hypothesis of no difference in binary responses between two treatment groups; and (2) the proportion of responders in each treatment group will be reported and differences between two treatment groups will be summarized by the weighted difference and its 95% confidence interval obtained by normal approximation. The difference in proportions will be calculated within each randomization stratum. The final estimate of the difference in proportions will be a weighted average of these stratum-specific estimates using CMH weights. The CMH weight w_k for stratum k ($k = 1, 2$) is given by,

$$w_k = \frac{\frac{n_{ik} n_{ck}}{n_{ik} + n_{ck}}}{\sum_{j=1}^2 \frac{n_{ij} n_{cj}}{n_{ij} + n_{cj}}}$$

where n refers to sample size, the subscript c refers to a comparator group (eg, placebo) and the subscript i refers to a test group (eg, an active treatment group). The difference is estimated as $\hat{d} = \sum_{k=1}^2 w_k (\hat{p}_{ik} - \hat{p}_{ck})$, where \hat{p} refers to the estimated proportion. An estimate for \hat{p} is obtained as x/n , where x is the number of responders.

Two-sided 95% confidence intervals for the difference (based on a normal approximation) are formed by:

$$\hat{d} \pm 1.96 \sqrt{\sum_{k=1}^2 w_k^2 \left(\frac{\hat{p}_{ik}(1 - \hat{p}_{ik})}{n_{ik}} + \frac{\hat{p}_{ck}(1 - \hat{p}_{ck})}{n_{ck}} \right)}$$

In the above formula, the standard error is $\sqrt{\sum_{k=1}^2 w_k^2 \left(\frac{\hat{p}_{ik}(1 - \hat{p}_{ik})}{n_{ik}} + \frac{\hat{p}_{ck}(1 - \hat{p}_{ck})}{n_{ck}} \right)}$. When the number of responders is zero ($x = 0$), then \hat{p} will be replaced by $0.5/(n + 1)$.

The 95% confidence interval for the response rate in each treatment group will also be provided using Wald normal approximation (or the Clopper-Pearson exact method when there are no or all responders in one group).

090177e1937d0b4eApproved\Approved On: 18-May-2020 15:17 (GMT)

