A method to analyze the longitudinal data of a binary endpoint measured during the placebo-controlled period (eg, IGA and EASI-75 response rates at Weeks 2, 4, 8, 12 and 16) under the MNAR assumption is called the tipping point analysis. This tipping point analysis

includes two popular scenarios as special cases: (1) the Jump-to-Reference (JTR) analysis in which the response rate for a missing subject assessment in the active treatment group takes on (ie, jumps to) the rate for the reference or control treatment group and (2) the MAR analysis in which the response rate for a missing subject assessment in each treatment group is based on the posterior predictive response rate for that treatment group alone.

The saturated logit-normal GLMM as described above will be used as the imputation model. Estimation of the model parameters will be performed under the Bayesian framework using Markov Chain Monte Carlo (MCMC) methods. We assign a non-informative prior for each component of β to be independent and identically distributed as $\sim N(0, 10000)$ and assign a weakly informative prior for σ^2 as an Inverse-Gamma distribution with shape=1 and scale=1. With this prior distribution, the 90th percentile for σ^2 is approximately 9.

Let $\beta^b, u_i^b, b = 1, 2, \dots, B$ be a sample from the posterior distribution. A single imputation $\widetilde{Y}_{i,j}^b$ of missing Y_{ij} is based on the posterior predictive distribution of the response probabilities estimated from the GLMM. For example, if subject i is randomized to PF-04965842 100 mg QD ($T_i = 1$), then at Week 12 ($V = 4$),

$$\text{logit}(\pi_{i,1,4}^b) = \text{logit} \left(P \left(\widetilde{Y}_{i,4}^b = 1 \mid T_i = 1, V = 4 \right) \right) = \beta_0^b + \beta_{11}^b + \beta_{24}^b + \beta_{341}^b + u_i^b.$$

If subject i is randomized to PF-04965842 200 mg QD ($T_i = 2$), then at Week 12 ($V = 4$),

$$\text{logit}(\pi_{i,2,4}^b) = \text{logit} \left(P \left(\widetilde{Y}_{i,4}^b = 1 \mid T_i = 2, V = 4 \right) \right) = \beta_0^b + \beta_{12}^b + \beta_{24}^b + \beta_{342}^b + u_i^b.$$

If subject i is randomized to dupilumab ($T_i = 3$), then at Week 12 ($V = 4$),

$$\text{logit}(\pi_{i,3,4}^b) = \text{logit} \left(P \left(\widetilde{Y}_{i,4}^b = 1 \mid T_i = 3, V = 4 \right) \right) = \beta_0^b + \beta_{13}^b + \beta_{24}^b + \beta_{343}^b + u_i^b.$$

If subject i is randomized to placebo ($T_i = 4$), then at Week 12 ($V = 4$),

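### The model that imputes missing responses for the supportive MAR and tipping point analyses omits baseline severity, although each imputed data set is analysed by severity stratum; the effect on the treatment difference is small and conditional

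*SAP*

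**What the plan says.** SAP 5.3.1 sets out the model fitted to the observed binary data: "Fixed factors will include treatment (PF-04965842 200 mg QD and 100 mg QD, dupilumab and the placebo group"), then "visit (Weeks 2, 4, 8, 12 and 16) and treatment-by-visit interaction". Within-subject correlation is handled by one further term: "A subject-specific random intercept will be used to model the correlation within a subject over time". Appendix 3 writes out the same linear predictor (intercept, treatment, visit, treatment-by-visit, subject effect) and states its use: "The saturated logit-normal GLMM as described above will be used as the imputation model". Neither place has a term for baseline severity or for any baseline value. The subject's sampled random effect is added to every imputed logit.

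For each completed data set, SAP 5.3.1 says the "CMH-weighted difference of proportions between each active group and placebo will be obtained along with the associated standard errors" by the methods of SAP 5.2.1. There the test is the "Cochran-Mantel-Haenszel (CMH) statistic adjusting for baseline disease severity (moderate or severe"), and the difference is a weighted average over two strata. SAP 5.2.1 calls these randomization strata. Protocol 4.3 says randomization is not stratified by severity, so I read them as the two baseline severity groups.

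Elsewhere the SAP does use severity: as a fixed effect in the MMRM (5.2.3), as a covariate in the ANCOVA (5.2.2) and as the stratification factor of the log-rank test (5.2.5).

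**The concern.** A variable that the analysis conditions on, and that may predict both response and dropout, belongs in the imputation model. Without it, the analysis labelled MAR (delta = 0) assumes that missingness is ignorable given treatment and the subject's observed responses, but not given severity. The MMRM for continuous endpoints makes the weaker assumption, so MAR means two different things in one SAP.

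Severity is a plausible predictor of response. Entry requires IGA of at least 3 (Protocol 4.1), and IGA response requires a score of 0 or 1 with a fall of at least 2 points. A subject who starts at 4 must therefore fall at least 3 points, and one who starts at 3 must fall 2.

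At stake is the supportive evidence on dropout for the two co-primary endpoints (SAP 6.1.2 and 6.2.2). If MAR holds given severity but severe subjects leave one arm more often, the MAR estimate is biased by the model rather than by the missing data.

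**Working it through.** **The plan's own figure.** SAP 2.2 assumes IGA response of 12% on placebo and a 20-point difference, with 200 active and 100 placebo subjects, two-sided 5%, and states at least 96% power.
- Unpooled SE = √(0.32×0.68/200 + 0.12×0.88/100) = √0.002144 = 0.0463.
- Pooled rate = (200×0.32 + 100×0.12)/300 = 0.2533, so the null SE = √(0.2533×0.7467×0.015) = 0.0533.
- Power = Φ((0.20 − 1.96×0.0533)/0.0463) = Φ(2.07) ≈ 98%, or 97.2% with continuity correction.

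The stated figure holds. The point does not depend on it, but the planning rates and the SE of 4.6 points set the scale below.

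**Simulation.** The model was fitted with and without severity to large simulated samples (60,000 placebo, 120,000 active) by marginal maximum likelihood, which stands in for the Bayesian fit. Week 12 dropouts were imputed from their own posterior for the random effect, and the SAP 5.2.1 difference was then taken. From the documents: 12% vs 32%, the model terms and the two strata. Assumed, because the documents do not give them: severe share 35% or 50%; severe-to-moderate odds ratio for response 0.6 to 0.25; random-intercept SD 2.5; dropout 6% to 30% by arm and severity; one quarter of dropouts with no post-baseline data.

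**What happens to imputed rates.** Active arm, 35% severe, odds ratio 0.4, flat 10% dropout:

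| Dropouts | Severity omitted | Severity included |
|---|---|---|
| Severe, all | 27.9% | 20.3% (true rate about 20%) |
| Severe, no post-baseline data | 31.9% | – |
| Severe, some visits observed | 26.5% | – |
| Moderate, all | 34.1% | 38.1% |

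For severe dropouts with observed visits, the random intercept closes (31.9 − 26.5)/(31.9 − 20.3) = 5.4/11.6, or about 47% of the gap.

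**Why it mostly cancels.** The shift in the active-arm rate is the sum over strata of severe or moderate share × dropout × change in imputed rate. Here 0.35×0.10×(+7.6) + 0.65×0.10×(−4.0) = +0.27 − 0.26, or about 0.0 points.

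**Shift in the treatment difference from omitting severity** (percentage points; each cell gives delta = 0, then delta = 1). Dropout is written moderate/severe.

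| Severe share, odds ratio | Flat 10% | Placebo 12/30, active 6/15 | Placebo 6/15, active 6/30 |
|---|---|---|---|
| 35%, 0.25 | −0.01; −0.01 | −0.05; −0.25 | +0.83; +0.19 |
| 50%, 0.6 | 0.00; 0.00 | −0.05; −0.12 | +0.37; +0.10 |
| 50%, 0.4 | 0.00; 0.00 | −0.10; −0.23 | +0.67; +0.18 |
| 50%, 0.25 | 0.00; 0.00 | −0.11; −0.32 | +0.97; +0.22 |

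Over all combinations tried, the delta = 0 shift was 0.0 with flat dropout, −0.04 to −0.11 in the middle pattern and +0.33 to +0.97 in the last.

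**Hand check of the largest value.** In the active arm, severe dropouts are imputed at 27.8% instead of 18.1%, and moderate dropouts at 38.0% instead of 45.8%. The active rate moves by 0.5×0.30×9.7 + 0.5×0.06×(−7.8) = 1.46 − 0.23 = +1.22 points. The difference moves by 21.03 − 20.06 = +0.97, so the placebo rate moves up by the remaining 0.25. Relative to the SE this is 0.97/4.6, or about 0.21.

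**Second set of inputs.** With 40% severe, Week 12 response of 58%/37% (moderate/severe) on active and 20%/9% on placebo, and random-intercept SD 2.2, the bias over four dropout patterns was −0.05 to +0.75 points without severity and −0.10 to +0.12 with it. These rates average 49.6% vs 15.6%, a 34-point effect that matches neither planning scenario, so they show the pattern only.

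**The case against.** The strongest reply is that this changes nothing that matters. The primary analysis counts dropouts as non-responders and never uses the model. The largest shift is about a fifth of a standard error. It needs a dropout pattern, severe subjects leaving the active arm disproportionately, that nothing in the documents predicts. The tipping point scan itself moves the estimate further: in the worst case above, going from delta = 0 to delta = 1 takes the difference from 21.03 to 17.48, or 3.55 points. All of this stands, and it limits the point to a supportive-analysis refinement.

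A reader might also infer stronger versions that the documents do not support.
- That severe dropouts are imputed at the mixed-severity rate. This is true only without post-baseline data, because Appendix 3 puts the subject's own random effect into every imputed logit.
- That the random intercept recovers severity only weakly because early visits are mostly non-response. The documents give no by-visit response rates, Protocol 1.2.4 reports rapid onset at 200 mg, and in the example about half the gap is recovered.
- That these are the only supportive analyses of the co-primary endpoints. SAP 6.1.2 and 6.2.2 also plan per-protocol analyses. That set requires observed Week 12 scores (SAP 4.2), so it does not test the dropout assumption, but it is another view that does not use this model.

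**Conclusion.** The mismatch is real and can be read directly from SAP 5.3.1, Appendix 3 and 5.2.1: the imputation model leaves out the one baseline factor on which the analysis stratifies. It pulls imputed rates for severe dropouts up and for moderate dropouts down, fully without post-baseline data and partly with it.

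The net effect on the treatment difference is about 0 when dropout is unrelated to severity or similarly related to it in both arms. It is at most about +1 point in favour of active at delta = 0 when severe active subjects drop out disproportionately. At delta = 1 it is −0.32 to +0.22 points, with no consistent direction.

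These sizes are conditional on the assumed severity mix, severity effect, dropout rates and share of dropouts without post-baseline data. It would be wrong to infer that the primary result is biased or that a trial conclusion would change; neither was shown. This is a minor improvement to a supportive analysis.

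**What to change.** Add baseline disease severity (moderate or severe), preferably with a severity-by-visit term, to the fixed effects of the mixed model in SAP 5.3.1, and to the linear predictor and the imputation formulas in Appendix 3. The analysis labelled MAR is then conditional on severity, in line with the CMH strata and the MMRM.

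The cost is one covariate, already collected, in a model already planned, plus a few parameters if the visit interaction is used. The primary analysis and the alpha allocation do not change. Protocol 9.2.3 names the mixed model without listing its covariates, so the change fits within the SAP.
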